2.2. OBJECTIVES AND SECONDARY EVALUATION CRITERIA

Secondary objectives

Compare between the 2 randomisation arms:

1. The evolution of pain intensity between the beginning of the treatment (D0), at 6 months (M6) and at 12 months (M12),
2. The presence of neuropathic pain and its evolution,
3. The evolution of isochrony between a physically executed and mentally simulated movement (Moseley, 2004; Moseley et al., 2008)
4. The evolution of anxiety and the presence of signs of the depressive series
5. The evolution of pain on muscle compression

6. The severity of the symptoms
7. Monitoring physical activity with activity trackers
8. The evolution of lean body mass measured on an impedance scale
9. The evolution of kinesiophobia
10. Changes in quality of life between the start of treatment (D0) and 12 months (M12)
11. Continuity of physical activity after the end of coaching

Secondary evaluation criteria

1. EVA at D0, M6 and M12
2. DN4 questionnaire score ≥ 4 at D0, M6 and M12
3. Difference between the duration of the performed movement and the imagined movement of picking up a magazine from a table at D0, M6 and M12
4. Hospital Anxiety and Depression scale (HAD) at D0, M6 and M12
5. Widespread Pain Index (WPI) (Häuser et al., 2017; Wolfe et al., 1990) at D0, M6 and M12
6. Symptom Severity Scale (SSS) (Häuser et al., 2017; Wolfe et al., 1990) at D0, M6 and M12
7. Percentage of success in achieving goals each month (M1-M12) as measured by activity tracker
 - (Duration in minutes per month at least 70% of the theoretical maximum heart rate $\times 100 / 240$ minutes
 - (4 weeks \times 60 minutes recommended = 240 minutes)
8. Percentage and weight of lean mass measured on an impedance scale at D0, M6 and M12
9. Tampa self-questionnaire (Knapik, Saulicz, & Gnat, 2011) at D0, M6 and M12
10. FIQR at D0 and M12 and EQ5D-5L at D0, M6 and M12
11. Level of physical activity between the groups between M6 and M12
 - (the duration in minutes per month between 50 and 60, between 60 and 70, between 70 and 80, between 80 and 90, and between 90 and 100% of the theoretical maximum heart rate measured with the activity tracker)

Exploratory secondary objective

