The isochrony between executed and imagined movement is a test inspired by the work of Moseley (2004) showing an alteration in the temporality of imagined movement in chronic pain patients. Patient positioning: initially, the patient has the upper limb and hand at the side of the body, with the feet 30cm from a table. A magazine is positioned by the operator flat, at the edge and not protruding from the table. First, the operator will ask the patient, "On my 'go' signal, you will take the magazine lying flat in front of you with your dominant hand and bring the limb back along your body at your comfort speed. When you have brought your limb back, you will say "stop". I will stop the clock at your end stop. This movement is to be done twice. The operator will note the 2 times in seconds and hundredths. In a second step, the operator will ask the patient: "At my starting "top", you will, without actually doing it and without moving, imagine taking with your dominant hand the magazine lying flat in front of you

and imagine bringing the limb back along your body at your comfort speed. When you have imagined bringing your limb back, you will say "stop". I will stop the clock at your end stop. This movement is to be done twice. The operator will note the 2 times in seconds and hundredths.

The Hospital Anxiety and Depression scale (HAD, Appendix 8) is a screening instrument for anxiety and depressive disorders. It consists of 14 items rated from 0 to 3. Seven questions relate to anxiety (total A) and seven others to the depressive dimension (total D), thus making it possible to obtain two scores (maximum score for each score = 21) (Zigmond & Snaith, 1983).

The Widespread Pain Index (WPI, Appendix 9) is a score given by the patient according to the number of affected areas (Häuser et al., 2017)

The Symptom Severity Scale (SSS, Appendix 10) is scored by the patient and includes headache, pain, cramp in the abdomen and depression (Häuser et al., 2017)

The percentage of target attainment will be calculated by averaging the attainment of monthly results, compared to clinical practice guidelines from the results recorded by the use of activity trackers

⇒ Duration in minutes per month at least 70% of the theoretical maximum heart rate x100 / 240 minutes
(4 weeks x 60 minutes recommended = 240 minutes)

The percentage (%) and dry mass (in kg) of lean mass will be measured on an impedance scale

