Analgesic and painkiller treatments: the consumption of analgesic and painkiller treatments in the week preceding the inclusion visits, M6 and M12 will be collected.

The Tampa Kinesiophobia Index Scale (TSK-CF, Appendix 7) was designed and validated to estimate the level of kinesiophobia present in an individual at the time of assessment, with the aim of adjusting the intervention accordingly, and subsequently assessing whether the intervention has had an effect on this common problem among people with persistent pain. The higher the score, the greater the level of kinesiophobia. A score of 40/68 is considered significant kinesiophobia (Vlaeyen et al. 1995), and the Tampa scale can also be used as a follow-up criterion.

Annex 11 consists of 2 pages: the **EQ-5D** descriptive system and the **EQ** visual analogue scale (EQ VAS).

The descriptive system consists of five dimensions: mobility, personal care, usual activities, pain/discomfort and anxiety/depression. Each dimension has 5 levels: no problem, mild problems, moderate problems, severe problems and extreme problems. The patient is asked to indicate their health

status by ticking the box next to the most appropriate statement in each of the 5 dimensions. The VAS EQ system records the patient's self-assessed health status on a vertical visual analogue scale, where the assessment criteria are entitled "The best health you can imagine" and "The worst health you can imagine". The VAS can be used as a quantitative measure of health outcomes that reflects the patient's own judgement.

The **level of physical activity** between the groups will be measured each month. It will be measured with activity trackers based on the time in minutes per month between 50 and 60, 60 and 70, 70 and 80, 80 and 90, and 90 and 100% of the theoretical maximum heart rate.

The activity trackers are OH1 wristbands from Polar™ (User Manual - Appendix 12). They retrieve, throughout the exercise, the heart rate of the subject thanks to optical sensors. The bracelet is either connected directly to a smartphone to record this frequency, or connectable to a computer in order to retrieve the data written in memory. There is no GPS on the bracelet. Patients will be specifically asked not to activate the GPS mode of the application if they are using a smartphone, in order to comply with the General Data Protection Regulation (GDPR) and data minimisation.

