4.5. STUDY SCHEDULE

TIMETABLE OF THE STUDY

Actions	J0 Inclusion visit	Between D0 and M6	M6	Between M6 and M12	M12
Patient information	X				
Collection of written consent	X				
Background	X				
Randomisation	X				
Clinical examination and questionnaires ¹	X		X		X
Encouragement to continue physical activity			X		
Physical activity with activity trackers		X	X	X ²	X ²
Analgesic treatments	X		X		X
Adverse events		X	X	X	X

¹EVA, DN4, HAD, WPI, SSS, impedance measurement, Tampa, FIQR, EQ-5D-5L

² Depending on the patient's choice

4.6. *IDENTIFICATION OF ALL SOURCE DATA NOT IN THE MEDICAL RECORD*

- Physical activity: practice at inclusion and type of activity
- Questionnaires: FIQR, DN4, Tampa, HAD, WPI, SSS, EQ-5D-5L
- EVA
- Physical activity during the study according to the randomisation arm (% success)
- Impedance measurement

4.7. *RULES FOR STOPPING A PERSON'S PARTICIPATION*

Criteria for premature termination of a person's participation in research

Any patient included in the protocol who no longer wishes to participate will be prematurely withdrawn from the study as soon as the request is made.

For the modalities and duration of the follow-up of the early leavers, see the statistical section.

- Withdrawal of patient consent at any time during the study, before publication of results.
Right to object to the use of the data at any time during the study, before publication of the results

Procedures for premature termination of a person's participation in research

For details of how to use the data of people who stopped the study prematurely, see the statistics section.

Criteria for stopping part or all of the research (excluding biostatistical considerations)

Part or all of the study may be stopped permanently or temporarily by decision of the ANSM, the CPP or the study sponsor.

A written confirmation will be sent to the coordinating investigator of the study (specifying the reasons for premature termination) and to the principal investigator of each centre if applicable.

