All variables will be described globally and by group. The description will include the numbers and percentages of modalities for qualitative variables and the minimum, maximum, mean, standard deviation and median for quantitative variables.

Main criterion

The patients' quality of life will be measured using the FIQR questionnaire at D0, M6 and M12. The evolution of the score at 6 and 12 months will be characterised by a graph and compared between the 2 groups using a linear regression model taking into account the baseline score at D0, the time effect, the "time*group" interaction and the repeated nature of the data.

The comparison of the evolution of the score at M6 will be tested from the M6 contrast.

Secondary criteria

The evolution of pain will be graphically characterised and compared using a mixed linear regression model taking into account the baseline data of the D0 score and the repeated nature of the data.

Neuropathic pain will be assessed using the DN4 questionnaire score. It will be compared between the two groups using a mixed generalized linear regression model taking into account the repeated nature of the data.

The evolution of the isochrony will be characterised graphically and compared using a mixed linear regression model taking into account the baseline data J0 and the repeated nature of the data.

The evolution of anxiety will be assessed from the total HAD score and compared between the two groups using a mixed linear regression model taking into account the baseline D0 score and the repeated nature of the data.

The evolution of pain on muscle compression will be assessed from the total WPI score and compared between the two groups using a mixed linear regression model taking into account the baseline score on D0 and the repeated nature of the data.

The severity of symptoms will be measured from the SSS score and compared using a mixed linear regression model taking into account the baseline data of the D0 score and the repeated nature of the data.

Physical activity monitoring will be collected every month until M12. Each month, the percentage of goal achievement will be calculated. The average percentage of success will be plotted and compared between the 2 groups using a mixed linear regression model taking into account the repeated nature of the data.

The evolution of lean body mass will be collected at D0 M6 and M12 and compared using a mixed linear regression model taking into account the repeated nature of the data.

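### The only tracker model pools the six programme months with the six months after, and criterion 11 (activity after M6) has no stated model

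*Combined protocol and SAP*

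**What the plan says.** Section 2.2 lists, among the comparisons between arms, "Continuity of physical activity after the end of coaching" (objective 11). The matching criterion is "Level of physical activity between the groups between M6 and M12", expressed as minutes per month in five bands from 50 to 100% of theoretical maximum heart rate. Section 4.3 adds that the level "between the groups will be measured each month" but gives no summary measure or contrast.

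The neighbouring criterion 7 is "Percentage of success in achieving goals each month (M1-M12) as measured by activity tracker". It counts minutes at or above 70% of theoretical maximum heart rate against a fixed target, "4 weeks x 60 minutes recommended = 240 minutes". Section 4.3 obtains the attainment figure by averaging the monthly results.

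The secondary-criteria part of section 5.2 says "Physical activity monitoring will be collected every month until M12", then plots the mean success percentage and compares it between arms in a mixed linear model for repeated data. That is the only tracker analysis in the plan. For the FIQR, by contrast, the same section names a baseline adjustment, a time effect, a time-by-group interaction and a contrast at M6.

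Two further facts matter. Section 4.6 lists "Physical activity: practice at inclusion and type of activity" as source data. The schedule in section 4.5 starts tracked activity after D0 and leaves it to the patient's choice after M6. Under section 4.2 the supervised programme lasts six months of the twelve.

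**The concern.** The rationale in section 1.1 expects a better medium- and long-term effect from personalised coaching. The tracker data are the only monthly evidence on whether activity differs once the programme stops. A single arm comparison over twelve months cannot tell an effect confined to the programme from one that lasts. Criterion 11 covers the right period but, with no model attached, its analysis would have to be chosen after the data are in hand.

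The tracker outcomes also have no tracked value from before randomisation. Section 3.3 does not exclude people who already exercise regularly (only previous participants in the association's programme). Some between-patient variation, and any chance imbalance in habitual exercise, therefore passes into the tracker comparisons, although a relevant baseline variable is collected.

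**Working it through.** **Inputs from the plan.** Monthly target: 4 x 60 = 240 minutes, as sections 2.2 and 4.3 state. Programme months: 6. Months after: 6. Attainment in a month = 100 x minutes / 240, counting minutes at or above 70% of theoretical maximum heart rate.

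**Assumed inputs.** The documents give no expected tracker minutes, so the following values are illustrative only: experimental arm 240 minutes per month in M1-M6 and 120 in M7-M12; control arm 120 minutes per month throughout; all months recorded.

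**Attainment by period.**

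| Arm | M1-M6 | M7-M12 | Average M1-M12 |
|---|---|---|---|
| Experimental | 100 x 240/240 = 100% | 100 x 120/240 = 50% | (6 x 100 + 6 x 50)/12 = 75% |
| Control | 100 x 120/240 = 50% | 50% | (12 x 50)/12 = 50% |
| Difference | 50 points | 0 points | 25 points |

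**General form.** Let d1 and d2 be the arm differences in M1-M6 and M7-M12. With complete data the pooled difference is (6 x d1 + 6 x d2)/12 = (d1 + d2)/2. If nothing lasts (d2 = 0), the pooled comparison still shows half of the programme-period difference, whatever its size. Here that is 50/2 = 25 points. Because tracked activity is optional after M6, patients may contribute fewer late months. A simple average over recorded months then leans further towards the programme period.

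**What each planned summary would show.** The M6-M12 level gives 120 versus 120 minutes, which is correct for that period. The pooled attainment gives 75% versus 50%, which is correct as a 12-month average but says nothing about persistence. A plot by month would show the fall after M6, but no planned estimate or test isolates it.

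**Baseline variable.** Of the tracker criteria, 7 has a model without any inclusion covariate and 11 has no model. Activity at inclusion is therefore used in neither.

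**The case against.** The strongest reply is that the plan is adequate as it stands. Criterion 11 isolates the period after M6, randomisation protects its between-arm comparison, and criterion 7 is computed and plotted month by month. Someone reading both would not mistake a programme effect for a lasting one. Taking account of repeated data could also be read as including month in the model. As for baseline, 1:1 randomisation and the description of all variables by group already address imbalance in expectation and make it visible; adjustment is mainly a gain in precision.

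Much of this stands. It limits the point to the missing analysis specification. It does not remove it: criterion 11 still has no model, and the tracker model omits the time terms that the same section spells out for the FIQR.

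A reader might go further and infer that criterion 11 is the wrong measure, because continuity must mean how much of their own M1-M6 activity patients keep. In the example, retention would be 120/240 = 50% versus 120/120 = 100%. The documents do not support that inference. Sections 4.2 and 4.5 use continuing activity in the sense of being active after M6, and section 2.2 frames the objective as a comparison of arms. A change from M1-M6 would also start from a level measured after randomisation, which the programme is meant to raise. In the example it is 120 - 240 = -120 minutes in the experimental arm and 120 - 120 = 0 in the control arm, so the arm that did more during the programme and the same afterwards would be scored as worse. It would further depend on who chose to keep using the tracker.

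**Conclusion.** The concern holds as a gap in the analysis plan. The only specified tracker comparison mixes six programme months with six months after. The criterion for the later period has no model, and activity practised at inclusion is unused.

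The size depends on the unknown d1 and d2. With equal, complete months, the pooled figure carries half of any programme-period difference into a 12-month result even when nothing persists; 25 points in the worked case rests on assumed minutes, not on trial figures.

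The documents do not show that criterion 11 is invalid, that the trial would wrongly declare no difference in continuity (no test of it is planned), or that the randomised comparison is biased for want of a tracker baseline. The FIQR primary analysis and the sample size are untouched. This is a low-cost improvement to secondary endpoints, best made before the tracker data are analysed.

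**What to change.** In section 5.2:

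1. Add month (or period: M1-M6, M7-M12) and its interaction with group to the tracker mixed model, and report the arm difference with its interval separately for each period.
2. State that the M7-M12 contrast serves objective 11. Goal attainment covers only minutes at or above 70% of theoretical maximum heart rate, so say also how the five-band minutes of criterion 11 are handled: the same model form, or description.
3. Adjust the tracker models for physical activity practised at inclusion.
4. Keep the between-arm M6-M12 level as criterion 11. Within-patient change from M1-M6 to M7-M12 may be shown as a descriptive supplement only.

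No new measurement is needed. The first cost is precision: each period uses 6 of the 12 months. With complete data and equal correlation between a patient's months, the standard error of a period difference lies between 1 times (months fully correlated) and sqrt(12/6) = 1.41 times (months independent) that of the pooled difference. The widening is slight if a patient's months are much alike. The second is that inclusion activity is recorded as practice and type, not as tracker minutes, so it is an imperfect covariate. Neither change resolves missing months after M6, since an absent record may mean no activity or no wear; the number of patients contributing to each period should be reported by arm.

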According to Bennet et al. (2009), a 14% decrease in quality of life since baseline is considered clinically significant (Bennett, Bushmakin, Cappelleri, Zlateva, & Sadosky, 2009). Evaluated in a cohort study of 10 patients (Hackshaw et al., 2016) the interest of a 37% improvement in quality of life following lifestyle coaching by nurses, physiotherapists and adapted physical activity teachers, encourages us to propose personalised coaching with a physical activity adapted to the patient and specific to her pathology. We believe that this solution would allow for adaptation to the patient's choice of physical activities, but would also allow for better individualised follow-up and better adaptation to the patient's physical and organisational constraints, with a better medium and long-term impact on quality of life.

We hypothesize an improvement in the quality of life of fibromyalgia patients in the medium (6 months) and long term (12 months) thanks to personalized coaching (specific physical activity).

The objective of our study is to compare the impact of two physical activity management in fibromyalgia patients at 6 and 12 months:

- 1. Control group: Traditional non-specific management in a common "multipathology" group, with activity trackers**
- 2. Experimental group: Specific management in a "fibromyalgia patients" group, with activity trackers**

1.2. *BENEFITS AND RISKS FOR RESEARCH PARTICIPANTS*

Benefits

Individual benefit

Physical activity improves pain, quality of life and body mass quality of patients.

We expect this innovative health sport coaching to optimise these improvements (in quality of life, pain and body mass quality) compared to standard patient management.

Collective benefit

- This new treatment modality will improve the care available to the algologist for the treatment of his patients.

- We also wanted to evaluate a new, simple and rapid test of kinesiophobia using isochrony between an imagined movement and an executed movement to predict a patient's adherence to physical activity management. If this test is effective, it will allow better targeting of patients who can benefit from a rehabilitation programme using physical activity coaching.
- Finally, an evaluation of an innovative patient monitoring with impedancemetry should make it possible to propose new monitoring tools for evaluating patients with fibromyalgia.

Risks

No excess risk due to participation in the study is expected

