Evaluating the isochrony between a physically performed and mentally simulated movement as a predictive test of improved quality of life following a physical activity programme Isochrony will be assessed by the difference between the duration of the performed movement and the imagined movement of taking a review on a table at D0. The quality of life of the patients will be assessed from the FIQR score at M6 and M12.

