4.3. RESEARCH AND ANALYSIS TECHNIQUES

Detailed description of the evaluation parameters

The revised Fibromyalgia Impact Questionnaire (FIQR, Appendix 5) is a self-administered questionnaire to assess the quality of life of the fibromyalgia patient (Burckhardt, Clark, & Bennett, 1991). Composed of 10 items, the first item includes eleven questions rated from 0 to 3 on a Likert scale. Items 2 and 3 ask the patient to indicate the number of days they felt well and the number of days they were unable to work (including housework) due to fibromyalgia symptoms. Items 4 to 10 are horizontal linear scales marked in 10 steps on which the patient rates work difficulties, pain, fatigue, morning fatigue, stiffness, anxiety and depression. The Minimum Clinically Important Difference is 14%. (Bennett et al., 2009). This means that a 14% difference in the FIQR score is clinically important.

The Visual Analogue Scale (VAS) of pain is used to assess the progression of pain (Scott & Huskisson, 1976). . The therapist should explain the use of the scale by presenting the ruler with the extremes: "You have to move the cursor, with no pain on the left and the maximum pain you can imagine on the right". It is marked from 0 to 100 on a ruler, the patient must move a cursor on the side without graduation. The therapist reports the intensity of the pain felt on the graduated side. The Minimum Detectable Change is 11, while the Minimum Clinically Important Difference is 13.7 points out of 100. The evaluation of the pain will be done on the different areas of pain felt by the patient (cervical, limb).

The DN4 questionnaire (Appendix 6) is used for the detection of neuropathic pain. The first part is based on the history, the second on a clinical examination. This questionnaire is administered by the therapist. If the score is greater than or equal to 4/10, the test will be considered positive (Bouhassira et al., 2005).

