
The evolution of kinesiophobia will be assessed using the TAMPA self questionnaire at D0, M6 and M12. The total score will be compared between the groups using a mixed linear regression model taking into account the baseline score on D0 and the repeated nature of the data.

The evolution of the quality of life will be measured using the EQ5D-5L questionnaire at D0, M6 and M12. The evolution of the score will be characterised by a graph and compared between the 2 groups using a mixed linear regression model taking into account the baseline score on D0 and the repeated nature of the data.

Exploratory criterion

The evolution of the FIQR score will be evaluated using a linear mixed model taking into account the group and repeated nature of the data as well as the isochrony data at D0 in order to evaluate its predictive character.

Statistical justification of the number of inclusions

The study is a superiority trial on the decrease of the FIQR score (improvement of the quality of life) at 6 months between a control group (classic non-specific management in a common "multipathology" group) and an experimental group (specific management in a "fibromyalgia patients" group).

According to Hackshaw et al. (2016), the mean baseline QoL of the ten patients included was 49.4 (13.8) on the FIQR scale. After 6 months of intervention (life coaching including physical activity), the mean level of quality of life was 31.0 (13.2), i.e. a decrease in score of 18.4 points (37% decrease).

Evidence of a 7-point difference between the two intervention groups at M6 will be considered clinically significant.

With a power of 80%, and an alpha risk of 5%, 114 patients will be needed to show this difference. To ensure the necessary power, an additional 10% of patients will be included, for a total of 126 patients.

Expected level of statistical significance

The alpha risk is set at 5%.

Statistical criteria for stopping the research

NA

Method of accounting for missing, unused or invalid data

All missing data and the reason for it will be described in each group.

The FIQR score will be estimated and compared between the 2 groups using a linear model taking into account the repeated nature of the data, so no imputation method will be applied.

Managing changes to the original strategy analysis plan

NA

Selection of persons to be included in the analyses

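### Exploratory objective: the mixed model planned for baseline isochrony shows association with FIQR, not how well it works as a predictive test; adding an AUC would be a cheap improvement

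*Combined protocol and SAP*

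**What the plan says.** The exploratory objective in section 2.2 is to evaluate isochrony between an executed and an imagined movement "as a predictive test of improved quality of life following a physical activity programme". The measure is a continuous time difference at D0: "Isochrony will be assessed by the difference between the duration of the performed movement and the imagined movement". The outcome is also continuous: "The quality of life of the patients will be assessed from the FIQR score at M6 and M12".

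The whole analysis is one sentence in section 5.2 (Exploratory criterion). It plans a linear mixed model for FIQR over time that allows for the arm and for repeated measurement, and the test enters only at the end of that sentence: "as well as the isochrony data at D0 in order to evaluate its predictive character".

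Section 1.2 (collective benefit) gives the motivation. There the test is meant "to predict a patient's adherence to physical activity management", and the hoped-for use is conditional: "If this test is effective, it will allow better targeting of patients who can benefit from a rehabilitation programme using physical activity coaching".

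Section 4.3 states a threshold for the FIQR, "This means that a 14% difference in the FIQR score is clinically important", and section 1.1 expresses the same 14% as a change since baseline. Neither place links it to the isochrony objective.

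For this objective the documents give no definition of an improved patient, no cut-off for the time difference, no measure of discrimination, and no criterion for calling the test effective.

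**The concern.** The objective asks a question about a test: does a patient's D0 result tell us whether that patient will improve? The planned model answers a question about averages: does mean FIQR vary with D0 isochrony? A slope can be clearly different from zero while the isochrony distributions of improvers and non-improvers overlap almost completely.

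If the plan is followed exactly, the report will contain an isochrony coefficient with its confidence interval and p-value, and nothing on discrimination. A statement about predictive character would then rest on the coefficient alone. If a responder definition or cut-off were added later, it would be chosen after seeing the data, when optimism is greatest.

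At stake is the interpretation of one exploratory result. The primary endpoint, the sample size and the handling of patients are not affected.

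**Working it through.** **Inputs from section 5.2.** 114 patients before inflation and 126 after; alpha 5%; power 80%; difference of 7 FIQR points; pilot SD at 6 months 13.2. The documents give no sample-size figure for isochrony and no distribution for it.

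**Step 1: the plan's own figure.** By the normal formula, n per arm = 2 × (1.960 + 0.842)² × 13.2² / 7², which rounds up to 56 (112 in total). The t-test version gives 56.8, so 57 per arm, or 114, which matches. 114 × 1.10 = 125.4, rounded up to 126. The match implies a two-sided test and SD 13.2, neither of which is stated as a design value. I use 114 as the number available.

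**Step 2: smallest significant correlation.** As a simplification, take one FIQR change per patient. Then r = t / √(df + t²).
- n = 114, df = 112, t = 1.981: r = 1.981 / √(112 + 3.926) = 0.184, R² = 3.4%.
- n = 114 with group also in the model, df = 111: r = 0.185, R² = 3.4%.
- n = 126 with group in the model, df = 123: r = 0.176, R² = 3.1%.

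**Step 3: what that means for a test.** Assume D0 isochrony and FIQR change are bivariate normal, and that 30, 50 or 70% of patients improve. Both are assumptions.
- At r of about 0.184, the AUC is 0.58 to 0.59 across the three shares.
- With half improving and a median cut, sensitivity = specificity = 0.5 + arcsin(r)/π = 0.5 + 0.185/3.142 = 0.559. Chance is 0.50.
- With 80% power the detectable correlation is tanh(2.80/√110) = 0.26. The AUC is then about 0.62, and sensitivity and specificity are about 58%.
- For comparison, an AUC of about 0.73 needs r of about 0.5.

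**Step 4: precision of an AUC in this trial.** Hanley–McNeil with A = 0.60, 57 improvers and 57 non-improvers:
- A/(2−A) = 0.4286 and 2A²/(1+A) = 0.45.
- Variance = [0.24 + 56 × (0.4286 − 0.36) + 56 × (0.45 − 0.36)] / 57² = 9.12 / 3,249 = 0.00281, so SE = 0.053.
- The 95% half-width is 1.96 × 0.053 = 0.10, an interval of about 0.50 to 0.70.
- With an assumed split of 91 improvers and 23 non-improvers, SE = 0.063 and the interval is about 0.48 to 0.72.

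**The case against.** **No decision rule is written.** A reader might infer that the plan would declare the test predictive once the slope reaches p < 0.05. The documents do not say so. The 5% alpha is a general statement, and the exploratory paragraph sets no success criterion. The gap is an absent criterion, not a wrong one. This objection stands and narrows the point.

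**Targeting is a conditional hope.** A reader might also infer that the result will decide who receives rehabilitation. Section 1.2 is conditional, describes possible future use, and speaks of predicting adherence, whereas section 2.2 concerns improved quality of life. No decision in this trial depends on the result. This stands too, and the two outcomes need reconciling.

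**An AUC does not settle targeting either.** Both arms receive physical activity (sections 4.2 and 4.3). Even a high AUC would be prognostic and would not show who benefits from activity. This stands and belongs in the fix.

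**Precision is limited.** One might hope the trial could sharply separate a weak test from a useful one. An observed AUC of 0.60 would carry an interval from chance to about 0.70, so it could not.

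**Association is a legitimate first step.** Modelling continuous FIQR is reasonable for a new test, and dichotomising at 14% discards information. That is a reason to keep the model alongside the AUC. It does not make the model an answer to a question about test performance.

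**Conclusion.** The point holds as a cheap improvement of minor severity to an exploratory objective. The plan poses a question of test performance and schedules only an association analysis. A coefficient that just reaches significance with 114 patients (r about 0.18, R² about 3%) is compatible with an AUC of about 0.58 to 0.59, close to chance.

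The AUC figures rest on bivariate normality, on assumed improvement shares of 30 to 70%, and on reducing the mixed model to one FIQR change per patient. They hardly move across those shares. The gap itself does not depend on them, because the documents plan no discrimination measure at all.

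**What to change.** In section 5.2 (Exploratory criterion):

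- Keep the linear mixed model and label it the association analysis.
- Base any statement about a predictive test on discrimination. Define improved as a FIQR reduction of at least 14% from the patient's own D0 value at M6. Report the AUC of D0 isochrony with its 95% CI, and the gain in AUC over D0 FIQR alone.
- Treat any cut-off derived from the data, with its sensitivity and specificity, as exploratory and internally validated.
- State that a significant slope alone does not establish a predictive test. State also that, with physical activity in both arms, the result is prognostic and does not show who benefits from activity.

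If the sponsor prefers not to add this, reword the objective in section 2.2 to association. In either case, reconcile section 1.2 (adherence) with section 2.2 (improved quality of life).

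**Cost.** A few sentences and a short extra analysis. Section 2.2 already schedules isochrony at D0 and the FIQR at D0, M6 and M12, so no visits or patients are added. The footnote to the section 4.5 timetable does not list the isochrony test among the D0 assessments and should be aligned. The downsides are some loss of information from dichotomising, an imprecise AUC (95% half-width about 0.10 with 57 and 57), and probably a less favourable claim for the test.
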